In order to assess the vascular effects of the supplement mix, we will perform a 2 armed parallel group, randomised, controlled, double blind clinical trial. Healthy subjects will be recruited and after reviewing a participant information sheet and signing the informed consent document randomised to either the supplement or placebo and consume it daily over 6 months (3-6 months \pm 1 month to ensure completion of study and allow flexibility for participants). The randomisation will be based on a sequential list with equal numbers of treatments A and B, with one being placebo and one verum. Recruited participants

will also be numbered sequentially and receive the respective treatment (A or B). The containers of treatments will be labelled with either A or B. The identity of what was A and what was B will be stored in a sealed envelope in a locked cabinet in [name] office. The measurements will take place in the morning, after an overnight fast and in the fasting stage, before and at 2 hours after the first dose and once in the morning fasted at 6 months. After measurements are completed, participants will be offered a breakfast snack and drink. Venous blood samples (<50 ml) will only be taken once on each study day.

The **primary endpoint** will be a change endothelial function as assessed by flow-mediated dilation (FMD) with ultrasound on the brachial artery.

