
Composition of supplement and placebo

The supplement mix is supplied as a powder to be mixed in water or other beverages like tea or coffee. The powder contains 12 ingredients, and it is commercially available (see also <https://novoslabs.com/>). All components are also part of a natural diet or are found naturally in the body. The supplement and matched placebo will be provided by AgeLess Sciences.

The composition is detailed in the table below. The placebo looks and tastes similar but does not contain the 12 supplements ingredients, only excipients and flavours.

Participants will receive a jar containing powder (supply of 6 months) with a spoon. Participants add one spoon of powder to 1 glass of water (240 ml), mix it and immediately drink it in the morning with breakfast. The participants will receive a paper diary to record at what time the supplement was consumed and if alone or with breakfast. If a dose is missed in the morning, they should just take it once they remember during the same day. If on a day the dose is missed entirely, we ask the participants to document this and carry on with the same amount on the next days but not take more than usual.

Table 1: Composition of one serving size (15 g) of supplement mix and placebo.

	VERUM Supplement mix	PLACEBO
Vitamin C (ascorbic acid)	100 mg	0
Magnesium (as magnesium malate)	304 mg	0
Calcium (as calcium alpha-ketoglutarate)	231 mg	0
Glycine	2,000 mg	0
Malate (as magnesium malate)	1,700 mg	0
Calcium alpha-ketoglutarate	1,100 mg	0
GreenGrown® glucosamine sulfate (vegan)	1,000 mg	0
Rhodiola rosea root extract (3% rosavins and 1% salidrosides)	300 mg	0
L-Theanine	150 mg	0
Hyaluronic acid	100 mg	0
Fisetin	100 mg	0
Organic ginger root extract (2% gingerols)	100 mg	0
Pterostilbene	50 mg	0
Lithium aspartate (providing 1 mg lithium)	20 mg	0
Other ingredients: Erythritol, malic acid, natural flavours, sodium bicarbonate, silicon dioxide, calcium silicate, stevia	X	X

“Overdosing” and adverse events

The recommended dose of the study supplement is 15 g which contains for example 100 mg Vit. C (approx. recommended daily intake 100 mg) and Lithium 1 mg (average daily intake). It is unlikely that participants will consume above the recommended dose as the supplement is insoluble in water if added in amounts above 15 g. However, to mitigate the unlikely occurrence of overconsumption, the following mitigation plan will be followed:

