- A diary will be completed to document the ingested amount every day and advise on not to take more than recommended.
- Training on preparing the solution will be conducted by the investigator staff on the first study day

Participants will be advised to call the investigator if they have consumed above the recommended dose or if any adverse event independent of dose occurs. The investigator will carefully assess any adverse events and advice accordingly and perform unblinding if required.

Sample size justification

The sample size is based on the primary endpoint FMD and the key secondary endpoints pulse wave velocity (PWV) and microvascular diameter.

Our previous experiments have shown average **FMD** values of 6% with standard deviation of 1%. While the supplement has not been tested in terms of effects on FMD, we expect a change in 1%. To detect this, we will need to study 17 verum subjects and 17 placebo subjects to be able to reject the null hypothesis that the population means of the verum and placebo groups are equal with probability (power) 0.8. The Type I error probability associated with this test of this null hypothesis is 0.05.

Our previous experiments have shown average **PWV** values of 9.3 m/s with the standard deviation of 1.3 m/s. While the supplement has not been tested in terms of effects on PWV, we expect a change in PWV of 1 m/s. To detect this, we will need to study 28 verum subjects and 28 placebo subjects to be able to reject the null hypothesis that the population means of the placebo and control groups are equal with probability (power) 0.8. The Type I error probability associated with this test of this null hypothesis is 0.05.

Our previous experiments have shown on average of **microvascular diameter using OCTA** of 48 μm with standard deviation is 6.4 μm . While the supplement has not been tested in terms of effects on microvascular diameter, we expect a change in diameter of 5 μm . To detect this, we will need to study 27 verum subjects and 27 placebo subjects to be able to reject the null hypothesis that the population means of the verum and placebo groups are equal with probability (power) 0.8. The Type I error probability associated with this test of this null hypothesis is 0.05.

Taken together, and taking 5-10% attrition into account we plan to recruit a total sample size of 60 (30 verum and 30 placebo).

Table 2: Schedule of events

Procedures	Visits (insert visit numbers as appropriate)

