------------	----------------------------------------------

STAMINA Study

	Screening (Visit 1)	Baseline (Visit 1)	Month 2 (Phone)	Month 4 (Phone)	6 (3-6±1) Months (visit 2)
Informed consent	x				
Screening/medical history	x				
Randomisation		x			
Demographics		x			
Questionnaires		x	x	x	x
Vascular exam		xx			x
Blood sampling		x			x
Spot urine		x			x
Treatment (supplement or placebo)		x			

10. Risk Assessment

1. Identified Risks	2. Likelihood	3. Potential Impact/ Outcome	4. Potential Severity of Outcome	5. Risk Management/Mitigating Factors	
Identify risks/hazards present	Identify how likely the event is i.e. Very likely/ Likely/ Possible/ Unlikely	Who might be harmed and how? Ensure you have considered the research team, participants and anyone not directly involved in the research.	Classify the severity of outcomes identified in 3. i.e. High/ Medium/ Low	Evaluate the risks and decide on the precautions.	Standard Operating Procedures*/ risk assessments Enter Ref no/ title/ expiry date
Data loss	Unlikely	The investigators and funders. Bad reputation for University and research team.	High	Data will be backed up and paper printout of CRFs stored.	
Data breach	Unlikely	The participants and investigators. Bad reputation for University and research team.	High	Data will be stored only with anonymous ID and only with "age" but not DOB in password protected file on university computers and drives. Paper copies stored in locked cabinet.	

STAMINA Study

1. Identified Risks	2. Likelihood	3. Potential Impact/Outcome	4. Potential Severity of Outcome	5. Risk Management/Mitigating Factors	
Incidental findings of medical condition	Possible	High blood pressure, cholesterol or glucose or other unexpected abnormal biochemical measurements could possibly be detected. Participant may require treatment.	Low (this may actually be a benefit for the participant as this may otherwise not have been detected)	PI will inform participant and offer to personally inform the GP to initiate treatment.	
“Overdosing”	Unlikely as supplement is not soluble in water in higher amounts.	Upset stomach	Low (no toxicity for components reported even in 10x amounts)	
 - Diary with instruction - Training by investigators how to prepare drinks 	

11. Data Management

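### All jars carry one of two letters with a single key, so one code-break or clue reveals the arm of every participant whose letter is known to the person who learns it

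*Protocol*

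**What the plan says.** Protocol section 9 (experimental design) calls the study a "randomised, controlled, double blind clinical trial". Allocation follows a sequential list with equal numbers of A and B, one letter being verum and the other placebo. Participants "will also be numbered sequentially and receive the respective treatment (A or B"). On labelling: "The containers of treatments will be labelled with either A or B". On the key: "The identity of what was A and what was B will be stored in a sealed envelope", which is kept in a locked cabinet.

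The subsection on overdosing and adverse events asks participants to call if they take too much or have any adverse event, whatever the dose. It continues: "The investigator will carefully assess any adverse events and advice accordingly and perform unblinding if required".

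Two statements suggest that breaks and clues may be rare. The subsection on composition says "The supplement and matched placebo will be provided by AgeLess Sciences". The risk table in section 10 gives the likelihood of overdosing as "Unlikely as supplement is not soluble in water in higher amounts" and rates its severity as low.

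The amendment history does not mention labelling, the key or unblinding.

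**The concern.** The letter on the jar is the treatment arm, and the only key described translates letters rather than participants. The protocol foresees unblinding during the trial but describes no means of revealing one allocation that leaves the others protected from a person who knows the letters. A convincing clue about one jar spreads in the same way to every jar with that letter.

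The primary endpoint is FMD by ultrasound, and carotid ultrasound supplies secondary endpoints. Both depend on the operator, and both are repeated at the final visit, months after allocation. If the person who acquires or reads those scans learned the key and knew the letters, every final exam still to be acquired or read would lose its blinding, not only that of the participant who needed it. Exams already acquired and read cannot be affected. Most blood and urine biomarkers go to an outside laboratory and are less exposed.

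**Working it through.** The protocol gives no figure on this point to reproduce. The check has two parts.

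**1. Reach of one break**

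Inputs from the protocol: 60 participants (30 + 30), two letters, one key.

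- As written: learning that A is one arm fixes B by elimination. For a person who knows all the letters, 30 + 30 = 60 of 60 allocations are decoded. For a person who knows only the affected participant's letter, 1 of 60 is decoded.
- With unique jar numbers and one code-break per participant: 1 of 60, provided staff no longer hold the A/B list. If they do, opening one participant's code-break shows what that participant's letter means, and the list then decodes the rest.

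**2. Final exams that could still be affected**

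The relevant count is of participants who already have a lettered jar and whose final exam is still to come.

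Assumptions, not from the protocol:
- entry is uniform over R months;
- the break is triggered by a randomly chosen participant at a uniformly random time in follow-up.

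Follow-up F is 6 months, the nominal duration in section 9.

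Let D be the difference between another participant's entry time and that of the trigger, and U the time from the trigger's entry to the break. The other participant is enrolled with the exam pending when U − F < D ≤ U. The density of D is (R − |d|)/R² and U is uniform on (0, F), so for F ≤ R

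P = (2 / (F·R²)) · ∫₀^F (R − d)(F − d) dd = F/R − F²/(3R²).

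The expected count, including the trigger, is 1 + 59·P.

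| R (months) | P, F = 6 | Count, F = 6 | P, F = 3 | Count, F = 3 |
|---|---|---|---|---|
| 6 | 1 − 1/3 = 0.667 | 40.3 | 0.5 − 0.0833 = 0.417 | 25.6 |
| 12 | 0.5 − 0.0833 = 0.417 | 25.6 | 0.25 − 0.0208 = 0.229 | 14.5 |
| 24 | 0.25 − 0.0208 = 0.229 | 14.5 | 0.125 − 0.0052 = 0.120 | 8.1 |

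The F = 3 columns use the short end of the 3 to 6 months that section 9 allows. These are average counts of exposed exams given that a break happens and reaches someone who knows the letters. They are not estimates of bias.

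**The case against.** The strongest reply is that the harm needs a chain of events that the protocol does not state. A break or clue must occur during follow-up, it must reach the person who scans or reads, that person must know the letters, and the knowledge must shift the readings. The protocol does not say who holds the list, hands out jars, opens the envelope or scans. The placebo is described as matched, and overdosing is rated unlikely and of low severity. This stands, and it limits the weight of the point. It does not remove it. The overdosing rating does not cover the other adverse events for which unblinding is foreseen. The letter is on the jar, the first dose is taken between two vascular exams at visit 1, and study staff train participants to prepare it. No shielding of the letters is described.

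Three stronger readings are tempting, and the protocol supports none of them.

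- *A reader might infer that no participant can ever be unblinded alone.* That is true only for someone who knows other participants' letters. A person without them can be told one allocation and learn nothing about the rest.
- *A reader might put a probability on a break.* The protocol gives no rate. With assumed rates of 0.1% to 2% per participant, 1 − (1 − r)^60 runs from 6% to 70%, so the answer is simply the assumption.
- *A reader might count every final exam still to come.* With F = 6 this averages 1 + 59·(0.5 + 0.5·P) = 50, 43 or 37 for R = 6, 12 or 24, always at least half of 60. But it includes people not yet enrolled, whose jars could still be recoded after a break. For those already enrolled, the count is below half at 12 and 24 months (25.6 and 14.5).

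**Conclusion.** The point holds in a limited form, as a cheap improvement. The link between participants follows from stated rules, two letters and one key, and not from a detail left out. One break or convincing clue can decode up to 60 of 60 allocations for a person who knows the letters, against 1 of 60 with individual codes.

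Given such a break, about 40, 26 or 15 enrolled participants would on average still await their final exam, with 6-month follow-up and recruitment over an assumed 6, 12 or 24 months. The counts are smaller with shorter follow-up. Whether any FMD or carotid reading would be biased depends on roles that the protocol does not state. Nothing in it shows that the blind has been or will be broken, or that the person who unblinds also scans. Only the protocol is at hand, but an analysis plan would not normally change container labelling or code-break.

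**What to change.** Three changes are needed together:

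- Label jars with unique participant or kit numbers instead of A or B, in an order that does not reveal the arm.
- Replace the single A/B key with one sealed code-break per participant.
- Replace the sequential A/B list used by study staff with a list of kit numbers only. The treatment list should be held by the supplier or by a person who does not enrol, measure or analyse.

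Without the third change, the first two do not contain a break.

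The cost is a protocol amendment, relabelling of up to 60 jars, up to 60 envelopes, and one person kept apart from enrolment, measurement and analysis. Sample size, visits and treatment stay as they are.

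The protocol does not state recruitment status. If recruitment has begun, apply the changes to unissued jars and acknowledge that issued jars remain linked by letter. Each participant receives a single six-month jar, so no planned resupply offers a chance to recode it. The benefit therefore shrinks with every jar issued. If no break ever occurs, the main gain is that a clue about one jar no longer carries over to others.

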Secondary endpoints will be change in blood pressure and arterial stiffness as determined by an upper arm cuff and optical sensors and ECG. Additional secondary endpoints are carotid artery stiffness, intima-media thickness as assessed by carotid artery ultrasound and microvascular structure and function with optical coherence tomography angiography (OCTA) as assessed in parallel with FMD measurements on the arm. As additional secondary endpoints, we will assess blood biomarkers of cardiovascular health including blood lipids (fasting total cholesterol, fasting LDL, fasting HDL, ApoB, fasting triglycerides, and fasting insulin) and glucose control (fasting glucose and HbA1c). A change in cardiovascular risk score will be another secondary endpoint. We will used the Heart SCORE2 estimate 10-year risk of a myocardial infarction, stroke or cardiovascular death, based on age, sex, smoking habits, systolic blood pressure and non-HDL cholesterol (<https://www.escardio.org/Education/Practice-Tools/CVD-prevention-toolbox/HeartScore>). A pre-specified subgroup analysis will be performed in people with intermediate-high (<1% estimated 10-year cardiovascular risk) and high (>5% estimated 10 year cardiovascular risk) baseline CV risk. We expect more pronounced effects of the supplement in people with higher risk i.e. higher blood pressure or cholesterol at baseline. **Exploratory tertiary endpoints** will include blood biomarkers of inflammation (high sensitivity C-reactive protein, TNF-alpha receptor II, Interleukin 6), platelet reactivity, DNA damage (measured via γ H2AX in blood and 8-hydroxydeoxyguanosine in urine), ageing (growth differentiation factor 15, adiponectin, leptin), liver (transaminases) and kidney function (creatinine, cystatin C). We also want to explore novel biomarkers of aging, including epigenetic and transcriptomic aging clocks (on DNA samples), RNA and protein expression. In this regard, we will ask participants to allow us to store surplus blood, serum, plasma, RNA and DNA samples for future studies. To explore potential effects on dental health, we will take a digital photo of the teeth. Funding for the analyses needs to be obtained separately in the future. Sample processing and storage will comply with HTA regulations (see attached STAMINA_Human Tissue Governance Application Form V1.0.docx). Most blood and urine biomarkers will be analysed by Affinity Biomarker Lab. Governance including MTA is currently being prepared. The measurements (except for venous blood draws) will be entirely non-invasive, pain-free and require a single session of approximately 3 hours on the first day and 1 hour at 6 (3-6) months. Additional exploratory endpoints will be physical activity based on step/distance covered software on participants cell phone if they have this, dietary habits as assessed by food frequency questionnaire and 24 food recall and quality of life based on standard SQL questionnaire, and the completion at the start and end of the study of 8 questionnaires that assess anxiety, depressive feelings, happiness and well-being, given various substances in the formulation could also impact brain health and could contribute to improved cognitive and mental functioning, such as magnesium, glycine and Rhodiola rosea. All questionnaires are in the appendix. Pre-specified subgroup analyses will be performed in people with healthier diet, estimated high polyphenol intake at baseline and very high physical activity. These people may exhibit a smaller effect of the supplement.

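### The protocol predicts that effects differ between subgroups, but the analysis it describes looks only within each subgroup, and the subgroups are undefined or inconsistently defined

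*Protocol*

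**What the plan says.** All the subgroup text is in section 9 of the protocol, in the paragraph on secondary and exploratory endpoints.

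- **Cardiovascular risk.** A pre-specified subgroup analysis is planned in "people with intermediate-high (<1% estimated 10-year cardiovascular risk) and high (>5% estimated 10 year cardiovascular risk) baseline CV risk". Risk is SCORE2, "based on age, sex, smoking habits, systolic blood pressure and non-HDL cholesterol". The expectation is: "We expect more pronounced effects of the supplement in people with higher risk i.e. higher blood pressure or cholesterol at baseline".
- **Diet, polyphenols, activity.** "Pre-specified subgroup analyses will be performed in people with healthier diet, estimated high polyphenol intake at baseline and very high physical activity". The expectation is: "These people may exhibit a smaller effect of the supplement".

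No threshold, score or step count defines the second set of groups. No test is named for any subgroup analysis. The protocol neither mentions an interaction test nor excludes one. The sample size justification covers only the overall comparisons, with 30 participants per arm.

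**The concern.** Each expectation compares two effects: larger here than elsewhere, or smaller here than elsewhere. The analysis described is placed inside the people who have the trait. It gives one effect estimate with nothing to set against it. If that estimate is then read through its own p-value, a small group will often look like a weak responder only because it is small.

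The definitions add to this. Whether a diet is healthier, polyphenol intake high or activity very high is left to an unstated cut-off, so the term pre-specified is not yet earned. The word baseline is attached only to polyphenol intake, although diet and physical activity are also measured as outcomes and Table 2 schedules questionnaires at baseline, months 2 and 4, and the final visit. Groups formed on values recorded after treatment starts would no longer be a clean randomised comparison. For cardiovascular risk, the group labelled intermediate-high is given as below 1%, and people between 1% and 5% belong to no group.

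The protocol says the data are meant to help plan future studies. A spurious contrast would point those studies at the wrong population.

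**Working it through.** **Inputs from the protocol (sample size justification).** FMD "values of 6% with standard deviation of 1" percentage point, expected change 1 point, so d = 1/1 = 1.0. PWV: 1 m/s on SD 1.3, so d = 0.77. Microvascular diameter: 5 µm on SD 6.4, so d = 0.78. Power 0.8, alpha 0.05, 30 per arm.

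**The plan's own figures.** A two-sided two-sample t-test needs 16.7, 27.5 and 26.7 per arm. These round up to 17, 28 and 27, as stated. The same test is used below. Overall FMD power with 30 per arm is 97%.

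**Assumptions.** Subgroup sizes are not given. I take one half, one third and about one quarter of 30 per arm (15, 10 and 8), balanced between arms, with an identical true effect in everyone. I also assume that the subgroup and the remaining participants are each tested at 0.05 and the two results compared. The protocol does not state that step.

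**Formulas.** Let p be power in the subgroup and q power in the rest. The two sets of people do not overlap, so the tests are independent.
- Significant in the rest only: q(1 − p)
- Exactly one significant: q(1 − p) + p(1 − q)

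**FMD, 30 per arm**

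| Subgroup / rest, per arm | p | q | Rest only | Exactly one |
|---|---|---|---|---|
| 15 / 15 | 0.753 | 0.753 | 0.753 × 0.247 = 19% | 37% |
| 10 / 20 | 0.562 | 0.869 | 0.869 × 0.438 = 38% | 45% |
| 8 / 22 | 0.461 | 0.900 | 0.900 × 0.539 = 48% | 53% |

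The rest-only column is the pattern that would be read as a smaller effect in the subgroup, as predicted for diet, polyphenols and activity. For PWV it is 25%, 42% and 49%. With 27 per arm, after the 10% end of the planned attrition, the FMD figures are about 19%, 40% and 52% (subgroups of 14, 9 and 7).

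**Interaction test, same effect in everyone.** The error rate is 5% per modifier by construction (simulated 4.8-6.0%). Over four independent modifiers it is 1 − 0.95⁴ = 18.5% for one endpoint.

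**Power of the interaction test.** Take the extreme case in which the full FMD effect sits in one group and none in the other. The non-centrality is 1/√(2/a + 2/b), with a and b the per-arm sizes, on 60 − 4 = 56 degrees of freedom.
- 15 / 15: 1.94, power 48%
- 10 / 20: 1.83, power 43%
- 8 / 22: 1.71, power 39%

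For PWV the corresponding powers are 31%, 28% and 25%.

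**The case against.** The strongest reply is that the protocol only names groups. It sets no test, no p-value rule and no comparison of significance between groups. Interaction terms and exact thresholds are often left to a statistical analysis plan, which is not shown here. This stands to a degree: a reader might infer that the protocol has chosen within-subgroup testing in place of interactions, and the text does not support that. What remains is that the one analysis described does not address the stated expectations, whatever another document may add.

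Three other stronger readings also fail.

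- A reader might say that none of the subgroups has cut-offs. The cardiovascular-risk groups do, at below 1% and above 5%. Their fault is inconsistency.
- A reader might take the 37-53% of trials with exactly one significant result as errors in the expected direction. They count both directions. Only the 19-48% figures match the prediction for diet, polyphenols and activity. For the risk groups the direction depends on their unknown sizes. If the high-risk group is the smaller one, low power works against the predicted larger effect. The below-1% and above-5% groups are also not complements, so the table does not describe them.
- A reader might object that SCORE2 includes age, sex and smoking while the rationale mentions blood pressure and cholesterol. That is how a composite score works, and replacing it would be a preference.

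It can also be argued that the word baseline was meant to cover the whole list, and that these analyses are tentative and promise no subgroup claim. Both are fair, and one added sentence would settle each.

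**Conclusion.** The point holds in limited form. The protocol expects differences in effect and describes an analysis that cannot show them. Three groups called pre-specified have no definition, and the risk cut-offs contradict their label and leave a gap.

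If the diet, polyphenol or activity groups were judged by separate tests, a false impression of a smaller effect would arise in roughly one trial in five for an even split, and in nearly half when the subgroup is about a quarter of participants. The interaction test gives one in twenty per modifier. These figures rest on the sponsor's FMD assumptions, my assumed subgroup sizes, balance between arms, a common true effect, and a comparison of significance that the protocol does not state. The mismatch between question and analysis, and the definition faults, need none of these assumptions. This should be corrected, but it does not touch the primary comparison.

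**What to change.** Replace the subgroup sentences in section 9 with text to this effect:

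*Effect modification will be assessed in all randomised participants by a treatment-by-modifier interaction term. Modifiers are baseline values only: SCORE2 for the risk hypothesis, and diet score, polyphenol intake and step count recorded before the first dose for the others, kept continuous where possible. Within-subgroup estimates with confidence intervals are descriptive, and no claim of a differing effect will be based on within-subgroup p-values. All these analyses are exploratory.*

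If risk categories are kept for display, reconcile the below-1% cut-off with its label and assign the 1-5% range. Any groups shown for diet, polyphenols or activity need their cut-offs written down before unblinding. Continuous modifiers make the test itself independent of cut-offs. The number of modifiers should be reported alongside the results, because the 5% error rate applies to each one separately.

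The cost is one paragraph of wording, with care that the step count used predates the first dose. The price is low power: about 39-48% for FMD and 25-31% for PWV even in the extreme case, so few subgroup claims will be possible and a null interaction must not be read as proof of equal effects.

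### A six-month supply of product does not cover a visit 2 window that runs to month 7, so highly adherent late attenders can be measured off product

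*Protocol*

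**What the plan says.** The relevant statements are all in protocol section 9.

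- **Supply** (Composition of supplement and placebo): "Participants will receive a jar containing powder (supply of 6 months) with a spoon". The dose is one spoon a day. After a day missed entirely, participants "carry on with the same amount on the next days but not take more than usual", so missed doses stay in the jar.
- **Dispensing** (Table 2): the treatment row is marked at baseline only. The contacts at months 2 and 4 are by phone.
- **Length of intake** (design paragraph): daily for 6 months, qualified as "3-6 months \pm 1 month to ensure completion of study and allow flexibility for participants".
- **Timing of visit 2** (Table 2): the column is headed "6 (3-6±1) Months (visit 2", which also reaches month 7.
- **Timing of visit 2** (endpoint paragraph): the measurements "require a single session of approximately 3 hours on the first day and 1 hour at 6 (3-6) months", without the extra month.
- **Diary** (Overdosing and adverse events): "A diary will be completed to document the ingested amount every day".

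Nothing in the protocol requires a participant to be still taking product at visit 2.

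**The concern.** The quantity dispensed and the visit window are both fixed in the protocol, and they do not fit together. The design paragraph applies the extra month to daily intake as well as to the visit date, so month 7 counts as treatment time for which no product is described. The upper limit of the window is also stated in two ways, month 7 and month 6.

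The people affected are those with the best adherence, because skipped doses leave a reserve that covers the gap. They are also the participants who say most about a sustained effect, and the two phone calls are there to raise compliance.

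FMD is measured before the first dose, 2 hours after it, and at visit 2. The 2-hour reading is untouched. Visit 2 alone carries the sustained half of the hypothesis in section 4. If the effect fades once intake stops, an in-window reading taken off product pulls the verum mean towards placebo, and nothing in the protocol would make that reading a deviation.

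**Working it through.** **Inputs.** Supply of 6 months, one 15 g serving a day, no catch-up dosing (Composition of supplement and placebo, with Table 1). Latest visit 2 at 6 + 1 = 7 months (design paragraph and Table 2). One month is taken as 365.25/12 = 30.44 days. Adherence is the share of days on which the dose is taken, assumed constant over time.

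**Supply against window.** The jar holds 6 × 30.44 = 182.6 servings. The window ends on day 7 × 30.44 = 213.1. The shortfall at full adherence is 213.1 − 182.6 = 30.4 servings.

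**Time off product.** The jar is empty on day 182.6 / adherence, so

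days off product = max(0, visit day − 182.6 / adherence).

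| Adherence | Jar empty on day | Days off product, visit at end of month 7 | Days off product, visit at month 6.5 (day 197.8) |
|---|---|---|---|
| 100% | 182.6 | 30.4 | 15.2 |
| 95% | 192.2 | 20.8 | 5.6 |
| 90% | 202.9 | 10.1 | 0 |
| 85.7% | 213.1 | 0 | 0 |

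The gap closes where 182.6 / adherence equals the visit day: at 6/7 = 85.7% for month 7 and at 6/6.5 = 92.3% for month 6.5. Visits up to month 6 are not affected at any adherence.

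**What it could do to power (assumptions only).** The protocol's own sample sizes reproduce with a two-sided two-sample t-test at 0.05 and 80% power: 16.7, 27.5 and 26.7, rounded up to the stated 17 (FMD), 28 (PWV) and 27 (OCTA diameter) per arm. The protocol gives neither the share of late attenders nor how fast an effect fades. As an outer bound, suppose a fraction f of the verum arm is measured after losing the whole effect, with the SD unchanged. The mean difference becomes (1 − f) times the planned one. With 27 per arm (30 less 10% attrition):

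| f | FMD | PWV | OCTA diameter |
|---|---|---|---|
| 0 | 0.95 | 0.79 | 0.80 |
| 10% | 0.90 | 0.70 | 0.72 |
| 20% | 0.82 | 0.60 | 0.62 |
| 30% | 0.71 | 0.49 | 0.51 |

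With all 30 per arm, FMD power is 0.97, 0.93, 0.86 and 0.76 for the same four values of f. These are illustrations, not estimates: complete loss of effect in every late attender is the worst case.

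**The case against.** The text and the arithmetic are not in dispute; the argument is over how much they mean.

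- *A single supply is inferred.* The protocol does not rule out overfill or a posted second jar, and the baseline mark in Table 2 could denote the first dose. This stands as a caveat. But neither arrangement is described, and there is no visit between the two at which product could be handed over.
- *The extra month is probably a leftover.* The Amendment History records a move from 6 (±1) to 6 (3-6) months, and the design paragraph also gives the last measurement simply as 6 months. That is plausible. The extra month still stands in the current design paragraph and in Table 2, and if it is a leftover, deleting it is the remedy proposed here.
- *The figures show the extreme day.* True. At month 6.5 the gap is at most about 15 days. Harm needs late attendance, high adherence, no overage and a fading effect all together.
- *The exclusion criteria in section 8 ask for a 21-day stop for these ingredients.* That is an entry rule and not evidence of how fast a vascular effect fades. If it were used as a benchmark, only a visit after about 6.7 months at full adherence, or at least about 95% adherence at the end of month 7, would reach it. This narrows the worst cases but does not remove the mismatch.
- *FMD has room to spare.* Largely correct: even with 20% of the verum arm losing all effect, FMD power stays above 0.80. PWV and OCTA diameter have no such reserve.
- *The diary shows last intake, and handling off-product readings belongs in the SAP.* Agreed, and the absence of such a rule is not criticised. The dispensed quantity and the window are still protocol matters.
- *The early side of the same window gives a wider spread of exposure.* That is a separate issue and does not answer this one.

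**Conclusion.** The concern holds, as a minor point. Followed as written, the protocol permits in-window visit 2 measurements up to about 30 days after the product has run out. This can happen only to participants seen after month 6, and at the month-7 limit only to those with adherence above about 86%. The conclusion assumes that one jar with no overage is all that is dispensed, and that the month-7 limit applies.

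Any effect on the result is towards no difference between arms in the sustained comparison; the acute comparison is unaffected. Its actual size cannot be worked out from the protocol, because the share of late attenders and the rate at which an effect fades are not given.

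**What to change.** Make the design, endpoint and composition paragraphs of section 9 and Table 2 agree, in one of two ways.

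1. **End the visit 2 window at month 6**, where the supply ends, by deleting the extra month on the late side. The endpoint paragraph already reads this way. The cost is a wording amendment and some loss of scheduling flexibility.
2. **Keep month 7 and dispense a seven-month supply at visit 1.** The cost is a wording amendment and about 30 × 15 g = 450 g (0.45 kg) more powder per participant.

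Neither option adds a visit or a data item. The daily diary already identifies the last intake before visit 2.
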